1. BACKGROUND AND RATIONALE

1.1 Background

Prostate cancer is the most common cancer in men in the United States with a lifetime risk of 16% and the second leading cause of cancer-related death in men in the United States. While patients with localized prostate adenocarcinoma have 5-year survivals that approach 100% per the Surveillance, Epidemiology, and End Results (SEER) Program database, outcomes are much more dismal in the metastatic setting with an estimated 5-year survival of 30% (1). Given this, there has been considerable effort to further understand the pathogenesis and genetic underpinnings of locally advanced and metastatic prostate cancer.

While the average age of diagnosis of prostate cancer is 66 years old (1), there is increasing evidence for inherited genetic susceptibility to prostate cancer, particularly in patients with advanced prostate cancer. The most common germline mutations seen are those in the DNA repair pathway, and more specifically, the homologous recombination repair pathway, including *BRCA1/2* which can predispose to not only prostate cancer, but breast, ovarian, pancreatic, and skin cancers. In addition to the known incidence of mutations in *BRCA1* and *BRCA2*, germline mutations have been noted in other DNA repair genes including *ATM*, *CHEK2*, *PALB*, and others. Prostate cancer has been also been previously reported in patients with Lynch syndrome, another inherited genetic syndrome due to mutations in either *MLH1*, *MSH2*, *EPCAM*, *MSH6*, and *PMS2*.

A large multi-institutional study evaluated the prevalence of germline DNA repair gene mutations in 692 men with metastatic prostate cancer unselected for age and family history from eight centers, results of which are shown in Table 1 (2). Germline DNA was isolated and used for multiplex sequencing assays to assess 20 DNA repair genes. The study demonstrated that 84 germline DNA repair gene mutations were identified in 11.8% of men in 16 genes. In men with Gleason 8-10 prostate cancer, the prevalence of germline DNA repair gene mutations is 6%. Mutations were found most frequently in the following genes: *BRCA2* (37 men, 5.3%), *ATM* (11 men 1.6%), *CHEK2* (10 men 1.9%) and *BRCA1* (6 men 0.9%).

Table 1. Pathogenic Germline DNA Repair Aberrations in Prostate Cancer.

	Germline Mutations in DNA Repair Genes	
Metastatic Prostate Cancer	n=84/692	11.8%
Localized Prostate Cancer	n=23/499	4.6%
Gleason 6	n=2/45	4%
Gleason 7	n=9/249	4%
Gleason 8-10	n=12/205	6%
NCCN Low-Intermediate Risk	n=4/162	2%
NCCN High-risk	n=19/337	6%
No Cancer Diagnosis	n=1433/53,105	2.7%

NCCN=National Comprehensive Cancer Network.

Given this data, the most recent iteration of the NCCN guidelines for prostate cancer, published in April 2019, notes “Germline genetic testing is recommended for all men with high-risk, very-high-risk, regional, or metastatic prostate cancer.” Additionally, it is recommended that patients with localized low or intermediate risk prostate cancer with a positive family history or presence of intraductal histology are recommended to undergo germline testing (3). In addition to the NCCN recommendations, there have been other published recommendations. At the Philadelphia Prostate Cancer Conference, an expert panel convened to develop guidelines for germline testing which is shown in Table 2 (4). With regards to germline testing in localized prostate cancer, a collaboration between AUA, ASTRO, and SUO recommended consideration of genetic counseling for patients with high-risk localized prostate cancer and a strong family history of breast, ovarian, pancreatic, or other GI tumors (5). It is important to note that there are discrepancies among these guidelines and the NCCN guidelines are primarily utilized by payers, including Medicare, to determine coverage for testing.

Table 2: Guidelines on Germline Testing in Prostate Cancer

Organization	Source	Guidelines
National Comprehensive Cancer Network	Prostate Cancer, Version 4.2019	
All men with high-risk localized, very-high-risk localized, locally advanced, or metastatic prostate cancer.
 
• Family history criteria and consideration to prompt genetic testing: A strong family history of prostate cancer consists of: brother or father OR• Multiple family members who were diagnosed with prostate cancer (but not clinically localized Grade Group 1) at less than 60 years of age or who died from prostate cancer• Ashkenazi Jewish ancestry• ≥ 3 cancers on same side of family, especially diagnoses ≤ 50 years of age: bile duct, breast, colorectal, endometrial, gastric, kidney, melanoma, ovarian, pancreatic, prostate (but not clinically localized Grade Group 1), small bowel, or urothelial cancer• Genetic testing in the absence of family history or clinical features (eg, high- or very-high-risk prostate cancer, intraductal histology) may be of low yield. The patient should be counseled to inform clinicians of any update to family history.

Expert Panel	Philadelphia Consensus Meeting Publication, 2017	
Men meeting any one of the following suggested criteria should undergo genetic counseling and genetic testing:
 
 • All men with prostate cancer from families meeting established testing or syndromic criteria for the following: 
 ◦ Hereditary breast and ovarian cancer syndrome (HBOC) (Consensus: 93%) ◦ Hereditary prostate cancer (HPC) (Consensus: 95%) ◦ Lynch syndrome (LS) (Consensus: 88%) • Men with prostate cancer with two or more close blood relatives on the same side of the family with a cancer in the following syndromes: 
 • Post-consensus discussion included consideration of age cutoff for this criterion. A specific age cutoff will require additional data, and age at diagnosis is important to inquire in the genetic counseling session with patients. 
 ◦ HBOC (Consensus: 93%) ◦ HPC (Consensus: 86%) ◦ LS (Consensus: 86%) • All men with metastatic castrate-resistant prostate cancer should consider genetic testing (Consensus: 67%). Post-consensus discussion also included consideration of testing men with metastatic, hormone-sensitive prostate cancer to identify germline mutations to inform potential future treatment options and cascade testing in families. • Men with tumor sequencing showing mutations in cancer-risk genes should be recommended for germline testing, particularly after factoring in additional personal and family history (Consensus: 77%).
American Urological Society	Clinically Localized Prostate Cancer: AUA/ASTRO/SUO Guideline, 2017	
 • The Panel recommends that clinicians take detailed family history of cancers and give consideration to patient referral for genetic screening and counseling for men with localized high-risk prostate cancer, particularly in the setting of family history of first-degree relatives with cancers of breast, ovary, pancreas, other gastrointestinal cancers, and lymphoma.

Given that prostate cancer is the most common cancer among men, the recommendation to test such a large population of patients has placed significant demands on health systems and clinical workflows. There is increased demand for trained genetics professionals to provide quality counseling and testing services. Genetic counselors are trained in assessing family history for genetic risk, ordering

appropriate genetic testing and interpreting the results, discussing appropriate cancer screening recommendations, and helping families adapt to genetic testing results. Unfortunately, access to these services is often limited, with the majority of the small workforce of genetic counselors and clinical geneticists often centered in urban and academic areas (6). In 2016, The Genetic Counselor Workforce Working Group estimated a 72% growth in the workforce between 2017-2026, with the demand for genetic counselors not expected to meet population equilibrium until 2024-2030 (7). This limited access may necessitate other healthcare clinicians, such as oncologists, primary care physicians, or urologists, taking on some of the responsibilities of genetic testing. With expanded clinician education which utilizes the expertise and guidance of genetic counselors, healthcare clinicians can deliver quality genetic counseling education with the support from the geneticists for questions or more complicated cases. Taken together, this highlights a critical need for expanding genetic services and developing novel approaches to care outside of the historic delivery model (10).

While germline testing in prostate cancer offers patients further information regarding their genetic risk of malignancy, it also has therapeutic implications. As discussed previously the most commonly detected germline mutations include *BRCA1*, *BRCA2*, *PALB2*, *CHEK2*, *ATM*, *RAD51*, which compromise the DNA repair or homologous repair pathway. This pathway is involved in the repair of double stranded DNA breaks and maintenance of genomic stability (2). In cells with deficiency in homologous recombination repair, inhibition of PARP results in cell death via synthetic lethality. In a phase 2 trial of olaparib, a PARP inhibitor, in patients with metastatic CRPC with homologous repair mutations, 88% (n=14/16) of patients demonstrated a response to olaparib (6). Based on these data, the FDA granted “breakthrough therapy” designation status to the PARP inhibitor olaparib in metastatic CRPC in 2016. PROfound, a phase III trial examining olaparib compared to standard of care enzalutamide or abiraterone in mCRPC patients with homologous recombination repair alterations. In the PROfound trial, the radiographic progression-free survival with olaparib was 7.39 months compared to 3.55 months in patients treated with either abiraterone or enzalutamide (HR 0.34, 95% CI 0.25, 0.47, p<0.0001). Based on the results of this study, the FDA recently granted approval for olaparib in the treatment of mCRPC that has progressed on abiraterone or enzalutamide harboring a somatic or germline alteration in an HRR gene.

1.2 Rationale

Given the prevalence of germline mutations in 10-12% of patients with advanced prostate cancer and the diagnostic and therapeutic implications of germline testing, improving the frequency of testing is greatly needed. Here, we propose a pilot study to improve germline testing among patients with prostate cancer via implementation of an in-clinic educational intervention on germline testing with a trained staff member. We will start by assessing baseline knowledge and attitudes on germline testing in prostate cancer among oncologists and urologists. An educational session will be provided for all oncologists and urologists to review germline testing guidelines. We will then screen clinics for patients with prostate cancer who meet criteria for germline testing per NCCN guidelines and offer them the opportunity to meet with the trained educator to review germline testing. Following this standardized educational session, patient's will be given the opportunity to consent for a commercially available germline genetic testing platform.

2. OBJECTIVES AND HYPOTHESES

2.1 Primary Objective(s) & Hypotheses

Objectives

- (1) To assess the feasibility of a patient educational program to improve germline genetic testing for eligible patients with prostate cancer.
- (2) To assess the effectiveness of a patient educational program with regards to increasing germline genetic testing rate among adult prostate cancer patients who are recommended to receive germline testing per NCCN guidelines.

Hypotheses

- (1) We hypothesize intervention will be feasible with successful recruitment of our target sample size.
- (2) We hypothesize that the rates of germline testing among patients recruited to the study will be higher than rates of testing among patients not enrolled in the study.

2.2 Secondary Objective(s) & Hypotheses

Objectives

- (1) To assess patients' baseline knowledge of germline testing and the change in knowledge of germline testing with the educational intervention.
- (2) To assess a patient's baseline attitudes towards germline testing and assess the impact of an education interventional on patient perceptions of germline testing.
- (3) To assess the impact of germline testing results on prostate cancer management.
- (4) To assess prevalence of pathogenic germline mutations in patient population.

Hypotheses

- (1) We hypothesize that the educational intervention will lead to an improvement in knowledge of germline testing.
- (2) We hypothesize that the educational intervention will lead to a more favorable attitude towards germline testing among patients enrolled in the study.
- (3) We hypothesize that the educational intervention will result in greater prescribing of targeted therapies given detection of germline alterations in the HRR pathway.
- (4) We hypothesize that the educational session will improve patient's perception and familiarity with germline testing.

2.3 Exploratory Objective(s) & Hypotheses

Objectives

- (1) To describe the demographic and clinical characteristics among all patients who received germline testing and subsequently, stratify by presence of germline mutations in cancer susceptibility genes.

Hypotheses

- (1) We hypothesize that patients with pathogenic germline alteration have more aggressive disease patterns in both the localized and advanced settings.

3. METHODOLOGY

3.1 Study Design – General Aspects

We will then screen genitourinary oncology clinics at UC San Diego Health System to identify patients who are eligible for germline testing. After approval from their treating physician, we will approach patients in the clinic and introduce the educational intervention, which will consist of a one-on-one in-person educational sessions reviewing the rationale and the risks and benefits of germline testing. A virtual educational session was added due to the COVID-19 pandemic and will ideally occur over the Epic video chat platform, Doximity video chat, but can also occur via telephone for patients who are unable to use video chat.

The educational intervention will occur with a clinical research coordinator who will be trained to educate on germline testing in prostate cancer. At the start of the session, the patient will be given a short questionnaire (Appendix A) to assess their understanding about germline and genetic testing, along with a Family History questionnaire (Appendix B). Following this, the session will then include a one-on-one review of an educational handout on germline testing in prostate cancer (Appendix E). The handout will provide a concise, yet comprehensive review of germline testing including:

1. Overview of genetic germline testing
2. Rationale for germline testing in prostate cancer
3. Implications of germline testing in terms of patient's clinical care
4. Implications to family
5. Overview of results including discussion of pathogenic germline mutation and variants of unknown significance
6. Discussion of benefits and risks of testing

Session Overview	
Time (approximately)	Objective
1-5 minutes	Introduction
10 minutes	Pre-intervention survey
5 minutes	Video
10 minutes	Review of brochure
5 minutes	Time for patient to ask questions
10 minutes	Post-intervention survey

The patient will then have an opportunity to ask questions. If a patient wishes to proceed with testing, they will sign the standard consent to proceed with germline testing and the patient's clinician will be notified of intent to proceed with germline testing. Patients can elect to decline testing, defer testing to a later time, or request referral to genetic counseling to discuss the testing. We will track patterns of patient decision making following the educational intervention. Upon a patient deciding to pursue testing, testing will consist of a prostate cancer germline panel with a commercially available blood or saliva-based assay. Following the educational intervention, the patient will be asked to complete a short patient education and satisfaction questionnaire (Appendix D). Upon receipt of the results, the coordinator will alert the patient's clinician, who will then share the results with the patient either in clinic or by phone. If the results show a

pathogenic germline mutation, the patient will be referred to see the UCSD cancer medical genetics clinic for consultation with a genetics counselor. Additionally, the patient can elect to see a genetics counselor independent of the test results once the test results are reviewed. If a patient pursues genetic testing, following receipt of results, the patient's clinicians will be asked to complete a short survey on to assess how the results of germline testing affected the patient's current and future management (appendix D). There will be capacity for patients to complete questionnaires electronically. Additionally, to systematically understand the scope of questions asked by patients which will provide opportunity to optimize the educational intervention, we will record the educational sessions.

3.1.1 Data Source(s)

This is a single center study of prostate cancer patients treated in the UC San Diego genitourinary oncology clinics. Data will be captured in secure RedCap database. Data to be captured including demographics, clinical characteristics, disease characteristics and results of study questionnaires.

3.2 Study Population

The target population for this study is patients older than 18, with prostate cancer who meet the NCCN criteria for germline testing and who have not undergone prior germline testing.

Subjects will include those patients seen at a facility in the UCSD Health System. Genitourinary oncology clinics will be screened 1 week in advanced for eligible patients. Recruitment procedures will also involve the review of subject records by designated study personnel (e.g., investigators and/or study coordinators) in order to identify potentially eligible subjects. Since Protected Health Information (PHI) will be accessed via the hospital's medical record database and scheduling system (e.g., EPIC/IDX) *prior* to contacting the potential subject about the research study, we have been granted a partial waiver of HIPAA authorization for access to PHI for purposes of prescreening only.

For patients who are eligible for the trial, the investigator will approach the subject and offer participation in the trial. Standard HIPAA authorization to collect research data from the subject's medical record will be obtained at the time of informed consent. Given the COVID-19 pandemic, we are conducting sessions both in clinic and virtually. This will primarily occur via video chat or telephone. Given that this is a low-risk intervention of an educational session, we believe that virtual consenting is also appropriate here given the current pandemic.

For patients who decline the intervention or have not been approached at the time of analysis, these patients will be considered a separate cohort for comparison to the intervention cohort.

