3.4 Exclusion Criteria

Patients are excluded from the study if they:

1. Have had prior germline testing.
2. Have somatic genetic testing that is positive for a possible germline variant.

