4.1.2 Definition of Comparison Exposure

The comparison group will include individuals with prostate cancer who meet criteria for germline testing however were not approached about participating in the intervention or were approached and declined participating in the educational intervention. In this context, germline testing education will be at the discretion of the treating medical team.

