4.2 Outcomes

Primary Endpoints

1. The proportion of patients who undergo germline testing among those who are enrolled to the study compared to the proportion of patients who undergo germline testing who were eligible, but not enrolled into this study during the study time period
2. Feasibility of implementing an educational intervention for men with prostate cancer at risk of having a hereditary cancer syndrome. This will be assessed by:
 - Accrual rate by month.
 - Proportion of patients who consent to educational intervention among those who are approached (stratified by whether consent was performed in-person or virtually).

Secondary Endpoints

1. Patient understanding of germline testing before and after the education intervention based on questionnaire responses.
2. Patient-reported opinions on germline testing before and after intervention, and patient-reported satisfaction after educational intervention based on questionnaire responses.
3. Physician responses regarding how the germline testing result changed patient management.
4. Prevalence of pathogenic germline mutations among study patients who undergo germline testing.

Exploratory Endpoints

1. Clinical factors (patient and family history, disease characteristics, and outcomes) that are associated with the presence of a germline mutation in a cancer susceptibility gene.

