4.3 Other Variables and Covariates

We will capture the following additional demographic, clinical, and disease variables:

- Demographic data: Age, Marital Status, Race, Ethnicity, Employment Status, Clinician, Primary Language, Country of Birth, Education Level.
- Previous medical history: Comorbidities, Smoking History, and Family History of Malignancies.
- Disease characteristics: Date of Diagnosis, Site of Disease, Site(s) of Metastasis, if applicable, Histology/Grade/Pathologic Parameters, PSA, Stage, Somatic Molecular Profile, Date of Collection of Tissue Analyzed, Type of Tissue Analyzed.
- Treatment data: Date of Surgery, Date of Radiation, Dose of Radiation, Systemic Therapy.
- Treatment outcomes data: Toxicity, Dose Reduction, Reason for Dose Reduction, Response, Progression, Survival.

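### Does the prescreening-only waiver leave the comparator half of primary endpoint 1 without data?

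*Combined protocol and SAP*

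**What the plan says.** Section 4.2 sets the comparator for primary endpoint 1 as "the proportion of patients who undergo germline testing who were eligible, but not enrolled into this study during the study time period". Section 4.1.2 defines the group as eligible men who "were not approached about participating in the intervention or were approached and declined participating in the educational intervention". Section 3.2 agrees: men who decline "or have not been approached at the time of analysis, these patients will be considered a separate cohort for comparison to the intervention cohort". Section 4.5.1 computes the proportion tested in each group, compares the groups' characteristics by Fisher's exact or Wilcoxon rank-sum tests, and compares the two testing proportions by Fisher's exact test.

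On access to records, section 3.2 states that "we have been granted a partial waiver of HIPAA authorization for access to PHI for purposes of prescreening only". For men who join the study it adds: "Standard HIPAA authorization to collect research data from the subject's medical record will be obtained at the time of informed consent". Section 5.1.2 repeats that the HIPAA waiver is for prescreening but describes it as being requested, and asks for a matching partial waiver of informed consent. On timing, section 3.2 says "Genitourinary oncology clinics will be screened 1 week in advanced for eligible patients", and section 3.4 excludes men who "Have had prior germline testing".

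**The concern.** The comparators have signed nothing, and the plan still needs two things from their charts: whether they were tested during the study period, and enough baseline information to compare them with the enrolled men. The stated waiver stops at prescreening, and authorization to collect research data comes only with consent.

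The prescreening look cannot stand in for the outcome. A man found eligible is untested at that moment, because prior testing excludes him. His later status needs a second look, made to ascertain an outcome, and for a decliner that look comes after he has been contacted.

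If staff had no authority for that look and this emerged only at analysis, the comparator half of one of the two primary endpoints would be in doubt. So would the comparison of characteristics, which is the plan's only check on imbalance in a non-randomised contrast. The two descriptions of the waiver's status add to the impression that access was not settled.

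**Working it through.** **The plan's own figure.** Sections 4.5.1 and 4.8 give a two-sided 95% interval width of 0.27 to 0.29 for n = 50 and observed proportions from 0.3 to 0.7, by the exact method. With x tested out of n, the lower limit is the 0.025 quantile of Beta(x, n − x + 1) and the upper limit is the 0.975 quantile of Beta(x + 1, n − x). Widths are taken from unrounded limits.

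| x of 50 | Proportion | Lower | Upper | Width |
|---|---|---|---|---|
| 15 | 0.3 | 0.1786 | 0.4461 | 0.2675 |
| 20 | 0.4 | 0.2641 | 0.5482 | 0.2841 |
| 25 | 0.5 | 0.3553 | 0.6447 | 0.2895 |
| 30 | 0.6 | 0.4518 | 0.7359 | 0.2841 |
| 35 | 0.7 | 0.5539 | 0.8214 | 0.2675 |

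The stated range reproduces. It describes the enrolled proportion alone, so the comparator access question cannot touch it. The documents give no comparator sample size, expected rates or power, so there is no between-group figure to check.

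**What the comparison needs against what the text covers.**

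| Item needed under 4.5.1 | Access described |
|---|---|
| Eligibility of non-enrolled men | Covered: prescreening (3.2, 5.1.2) |
| Testing status at the first look | Untested for every eligible man, through the exclusion in 3.4 |
| Testing status later in the study period | Not described for men who have not consented |
| Characteristics to compare | Partly seen in judging eligibility; research abstraction not described |
| Enrolled men's data | Covered: authorization at consent (3.2) |

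The third row is the gap, with part of the fourth. It lies in what the protocol says about permission. The documents do not say that a wider approval was refused or is absent.

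**Does the gap alter the analysis?** Write a for enrolled men tested out of 50, and c for comparators tested out of m. Fisher's test uses the table (a, 50 − a; c, m − c) and nothing else. The approval under which c and m were obtained does not enter the p-value or either proportion. Citing an approval would leave all of them as they are.

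**Would the check on imbalance disappear if only de-identified counts could be had?** Not necessarily. Fisher's test on a categorical characteristic needs only counts per category in each group. A rank-sum test can be run on banded counts, with ties. The check is lost only if the counts are limited to tested and not tested. Producing such counts would still require someone permitted to read the individual charts, so this route does not remove the need for permission.

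**The waiver's status.** Section 3.2 has it granted; section 5.1.2 has it being requested. Both give the same scope, and no analysis depends on which is current. A likely reading is that 5.1.2 kept the wording of the application.

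**The case for a change.** The strongest case for a change is that the protocol should not, on its face, exclude access to its own primary comparator. Section 3.2 says prescreening only. Section 5.2.1 wants signed consent before study procedures, including completion of case report forms. Section 3.5 describes follow-up from the medical record only after the educational session, which means enrolled men only. Calling the work a quality improvement initiative does not help, because section 5.1.2 treats it as research that needs both waivers. Repeated prescreening before later appointments would show testing in some never-approached men, but would miss those with no later appointment. Citing an approval would cost almost nothing.

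All of that stands as a description of the text. If no approval for reading comparator charts existed, the comparator proportion, the test of testing rates and the comparison of characteristics could not be produced from individual records.

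What does not stand is the step from a missing statement to a faulty plan. Such approvals are held in ethics board papers outside these documents. Counting the data items listed for prescreening does not measure the gap either: that list is plainly incomplete, since eligibility cannot be judged without knowing about earlier germline testing. Nor does the length of the list in section 4.3 ("We will capture the following additional demographic, clinical, and disease variables"), because it includes treatment outcomes such as response and survival, which are not baseline characteristics for a check on imbalance.

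**Conclusion.** The protocol does not say under what authority comparator outcomes and characteristics are read, and it gives two statuses for one waiver. The first is a gap in regulatory documentation that the study team and its ethics board settle in their own papers; the second is a clerical slip. Neither makes a number, rule or analysis in the plan wrong. The effect on the enrolled proportion, its exact interval and the feasibility endpoint is nil. The effect on the comparator proportion and Fisher's tests is also nil when section 4.5.1 is carried out as written.

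This rests on one assumption that the documents can neither confirm nor refute: that permission to read comparator charts for the outcome and baseline data exists, or is obtained, before abstraction. If it were refused, the comparator half of primary endpoint 1 would be at risk, and how much survived would depend on what de-identified counts could lawfully be supplied. That is a matter for the approval file. It gives no reason to alter the endpoint, the comparator definition or the tests.
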